Title: TIP TOP (Tobacco Intervention in Primary Care Treatment Opportunities for Providers)**Abstract**

Most smokers do not make a quit attempt in any given year. For those who do, use of evidence-based treatment, including the use of nicotine replacement therapy (NRT) is modest at best. Brief physician advice to quit, based on the 5As/5Rs model, while offering some efficacy, is inconsistently administered and thus has limited population impact. There is a clear need for more efficacious methods, particularly in the clinical setting, to promote quitting. Our team recently completed a large, nationwide clinical trial of NRT sampling, i.e., testing whether brief provision of NRT promotes further uptake of cessation behavior, higher incidence of quit attempts, and higher rates of abstinence. The results of that trial were promising for all outcomes, and suggested that NRT sampling works by increasing both motivation and confidence to quit and increasing familiarity with NRT products as an option for quitting.

NRT sampling, when added to physician advice to quit, is uniquely suited to busy primary care settings for several reasons. First, primary care represents a prominent point of healthcare contact for a large number of smokers. Second, the sampling intervention is simple, takes only a few minutes to deliver, and requires minimal instructions. Third, unlike other clinic-based strategies such as motivational advice, NRT sampling is behaviorally based, and offers providers and patients, both of whom are often frustrated by persuasive messaging, a concrete experience to catalyze quitting. Fourth, sampling is supported by numerous quitline studies that show that free medications significantly increase call volume and cessation. Finally, sampling has a strong theoretical foundation to suggest that brief exposure to a product promotes wider acceptability of it.

This competing renewal proposes a translational comparative effectiveness trial, testing standard care (Ask, Advise, Refer) vs. standard care + NRT sampling (2wk supply of both nicotine patch and lozenge). Working within an established network (based at our institution) of primary care providers who have all established infrastructure for coordinating clinical research, smokers will be recruited directly within clinic practices. Interventions will be delivered by clinic personnel, and prospective follow-up will be centrally coordinated by our research team, using established procedures that yield high rates of retention. Though we track a number of outcomes, our primary aims are to examine the impact of NRT sampling on smoking behavior: cessation, quit attempts, uptake of additional evidence-based treatment.

Long, intensive treatments that combine behavioral and pharmacologic treatment have strong empirical support. However, they offer only partial utility because they do not readily lend themselves to real world primary care settings, where providers have limited time and expertise to address tobacco dependence. Improving the effectiveness and reach of brief intervention within primary care, as could be accomplished by NRT sampling, could have a major impact on population quit rates.

Project Narrative

The primary care setting offers a powerful opportunity to identify smokers and engage them in the quitting process, with the ultimate goal to lower the burden of preventable disease. Based on significant and promising findings from a recently completed randomized clinical trial, this comparative effectiveness trial will test whether NRT sampling, i.e., provision of starter-kits of nicotine replacement therapy, when combined with standard physician advice to quit, results in significant improvements in smoking-related outcomes (abstinence, quit attempts, use of additional quit resources) as compared to quit advice alone. Positive findings could offer both clinical and policy significance.

Specific Aims:

Smoking cessation rates have stagnated in the past decade. The ratio of ex- to ever-smokers (quit ratio) has plateaued, and smoking prevalence, once on a steady decline, has decreased <5% in the past 10 years. While smokers claim to be motivated to quit, fewer than half make a quit attempt in any given year, a statistic that has not demonstrably changed in over a decade. Cessation medications are significantly underutilized, in large part due to lack of knowledge that products even exist, how they work, and misperceptions about safety and efficacy. New and stronger efforts are needed to engage smokers in the quitting process, to increase the incidence of quit attempts, promote wider uptake of evidence-based treatment, and to promote cessation.

The primary care setting offers a powerful opportunity to identify large numbers of smokers and engage them in the quitting process, with the ultimate goal to promote quit attempts and cessation and lower the burden of preventable disease. Most smokers visit a doctor annually, and all practice organizations (e.g., Amer. Academy of Family Physicians) endorse evidence-based guidelines for treatment of tobacco dependence. Yet in the context of a busy and often over-burdened clinical setting, many physicians have limited time and other resources to effectively treat tobacco users. Novel interventions that are both brief and efficacious are needed to engage smokers in the quitting process and enhance quitting behavior.

Our study group has extensive experience developing and testing novel, behavioral-based interventions to prompt quitting. We recently concluded a large (N=849) nationwide, population based randomized clinical trial (RCT) testing the concept of NRT sampling, i.e., providing brief samples of over-the-counter nicotine replacement therapy with minimal behavioral instructions on use. NRT sampling was hypothesized to increase self-efficacy and motivation, and to familiarize smokers with and facilitate positive attitudes toward medication. The study sample consisted exclusively of smokers with no current interest in quitting (i.e., unmotivated smokers). This efficacy trial of cessation induction was powered on quit attempts, with secondary outcomes of abstinence. NRT sampling significantly increased the incidence of quit attempts, and there were strong trends for increased abstinence. NRT sampling worked through hypothesized mediators noted above. Based on these promising findings, we now propose a translational comparative effectiveness study, i.e., to disseminate and test our intervention into real world clinical practice, within the primary care setting to fully test (i.e., powered on abstinence) the concept of NRT sampling as an added component of standard care.

Our **Primary Specific Aim** is to examine cessation outcomes of a large-scale (N=1300; 20 participating clinics) randomized clinical trial of 1) Standard Care, based on established guidelines (Ask, Advise, Refer [quitline referral]) vs. 2) Standard Care + NRT Sampling. Participants will be drawn from a network of primary care settings that has established infrastructure in which to embed clinical research. Randomization will be at the clinic level, but individual participants represent the unit of analysis. Identified smokers who meet eligibility criteria will be consented into a trial. Interventions will be delivered within the primary clinic directly by providers who are trained and monitored on study procedures. All participants will receive advice to quit and referral to state quitlines. Half of the sample will receive a small token bag that includes samples (i.e., 1-2 week starter kit) of both nicotine patch and lozenge. Follow-up assessment (through 6 months) will track both primary (abstinence, quit attempts, use of additional treatment) and secondary (motivation, confidence) outcomes. Our team has strong experience in such trials, including methods to efficiently recruit and effectively retain large numbers of smokers in clinical research. Our principle hypotheses are as follows:

Hypothesis 1a: As compared to Standard Care model of physician-delivered brief advice (Ask, Advise, Refer), provision of brief advice + NRT samples within primary care setting will result in a higher abstinence rates (7-day, point prevalence at 6 month follow-up).

Hypothesis 1b: Brief advice + NRT sampling will result in longer period of abstinence (longest # days non-smoking) across the entire study duration.

Hypothesis 2: NRT sampling will result in higher rates of quit attempts (any self-defined and any 24hr quit attempt).

Hypothesis 3: Brief advice + NRT sampling will result in higher subsequent uptake of evidence-based treatment (behavioral, pharmacological assistance).

NRT sampling represents a brief, concrete, easy to explain strategy that both healthcare providers and smokers readily accept. Thus, it is uniquely suited to the primary care setting, and could be a novel, behaviorally based intervention to promote quitting. If so, NRT sampling holds great significance on both a clinical and policy level.

Human Subjects Research**1. Risks to Human Subjects****1.1 Human Subjects Involvement and Characteristics**

General Inclusion / exclusion criteria are as follows:

- a) age ≥ 18
- b) daily (25+ days within past 30) cigarette smoker of ≥ 5 cigs/day
- c) English speaking
- d) recruited through primary care sites aligned with study
- e) no FDA contraindications for use of NRT:
 - a. not pregnant, breastfeeding, or planning to become pregnant
 - b. no recent (past 3 months) cardiovascular trauma: MI, stroke

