4.1 Summary of the Protocol

The design calls for a 2-group, randomized clinical trial of 1) standard care (Ask, Advise, Refer) vs. 2) standard care + NRT sampling. Randomization will be at the clinic level, but the unit of analysis is the individual smoker. Following consent, baseline assessment, and provider intervention (all done within clinic), follow-up assessment (coordinated centrally through our study team) will continue at +1, +3, and +6 months. The primary outcome will be 7-day point prevalence abstinence at 6-month follow-up, though we track a number of other outcomes as well. A recent trial of comparative effectiveness for single/combined pharmacotherapy (79) provided strong framework for our decisions. As a comparative effectiveness study, our guiding philosophy is to optimize ecological (i.e., external) validity, while at the same time maintaining basic standards of scientific rigor.

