4.2 Primary and secondary outcomes

The primary outcome on which our study is powered is 7-day point prevalence at 6 month follow-up, which, unlike continuous abstinence, allows for delayed quitting. Unlike traditional cessation trials, there is no uniform quit date for all participants in the current trial, and thus anchoring abstinence to a designated quit attempt is unrealistic. However, we will track a number of secondary outcomes, including 30-day point prevalence abstinence, and incidence, frequency, latency, and duration of quit attempts (both self-defined and those lasting >24hrs), as well as smoking reduction (% reaching 50% reduction between baseline and end-of-study), provider acceptability and cost-effectiveness.

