4.9 Data Analysis Plan

All analyses are based on an intent-to-treat approach, and are nearly identical to analyses from our current and prior studies. Exploratory analysis will be performed on all variables to determine if transformations are needed. Any significant baseline differences between groups will be included in regression analyses described below. All analyses below will be run separately for full intent-to-treat sample (immediately below), per protocol, and, within the NRT group, using those participants who used single vs. combined NRT products.

Examination of Potential Site Differences Outcomes and patient characteristics will be estimated across clinics using summary statistics and confidence intervals. This will be considered an exploratory analysis due to the relatively large number of clinics and, hence, the large number of multiple comparisons that could arise. Grouped logistic regression modeling may be used to describe associations between clinic characteristics and binary clinical outcomes (e.g., quit rate).

Missing Data & Dropout The most conservative approach for handling missing data is to substitute them with baseline values, assuming outcomes have all returned to baseline, with no quit attempts made or abstinence achieved. If this assumption is incorrect, it biases the results towards the null by reducing between group differences. Since we expect few missing data, we will use this approach. If missing data >10%, we will calculate results using this conservative method but also using methods in which missing data are imputed as described in the SRNT guidelines. We will also assess whether dropout is differential by study group. In our current and recent studies of cessation induction, this has not been the case. Abstinence will be reported both with and without (missing samples) cotinine verification.

Hypotheses 1a, 2, & 3 These hypotheses predict that provision of NRT samples will lead to higher abstinence rates (Hyp. 1a), incidence of quit attempts (Hyp. 2), and uptake of additional treatment (Hyp. 3). Logistic regressions will be performed for each outcome with treatment group (standard care vs. NRT sampling)

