as the covariate, estimated using generalized estimating equations (GEE) to account for clustering within clinic. Rates for each outcome will be estimated along with its 95% confidence interval. The coefficient on group will be evaluated using a Wald test to determine if the abstinence rates in the two arms are statistically significantly different at the one-sided 0.025 level. Additional regression modeling will be performed where covariates such as age, gender, and race are accounted for. We will also consider interactions between NRT and categorical covariates to determine if there are certain subgroups in which NRT sampling is more or less effective. Though we expect few individuals to make more than one quit attempt over the span of 6 months, and thus examine incidence of quit attempts (Hypothesis 2), we will examine the distribution of quit attempts, and if appropriate, examine number of quit attempts via Poisson regression modeling. In addition to binary outcomes of treatment uptake (Hyp. 3), we will test for continuous outcomes (e.g., treatment intensity, duration) via GEE regressions.

Hypotheses 1b Hypothesis 1b predicts that provision of NRT samples will result in longer period of abstinence (longest # days non-smoking) across the entire study duration, and will be evaluated using regression modeling via GEE accounting for clustering by clinic.

Secondary Analyses

Provider Acceptability We will provide separate, descriptive data on provider acceptance and satisfaction with treatment delivery. We do not plan any formal between group comparisons because of very limited sample size (14 clinics in each site). This study is not powered on provider-level outcomes of our intervention, but such data will be useful as we consider expanding our intervention into different venues.

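### The Specific Aims list three primary outcomes while sections 4.1 and 4.2 name one, and section 4.9 does not say which result carries the trial's conclusion

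*Combined protocol and SAP*

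**What the plan says.** The Primary Specific Aim paragraph of the Specific Aims says that follow-up will track "primary (abstinence, quit attempts, use of additional treatment) and secondary (motivation, confidence) outcomes". The Abstract is worded in the same direction: "our primary aims are to examine the impact of NRT sampling on smoking behavior: cessation, quit attempts, uptake of additional evidence-based treatment".

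The Data and Safety Monitoring Plan says something else. Section 4.1: "The primary outcome will be 7-day point prevalence abstinence at 6-month follow-up". Section 4.2: "The primary outcome on which our study is powered is 7-day point prevalence at 6 month follow-up". It then continues: "we will track a number of secondary outcomes, including 30-day point prevalence abstinence, and incidence, frequency, latency, and duration of quit attempts". Treatment uptake does not appear in the 4.2 list, and neither does the longest abstinent period of Hypothesis 1b.

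Section 4.9 has one paragraph for Hypotheses 1a, 2 and 3. It fits a separate logistic model to each outcome by GEE with clustering by clinic, and applies a Wald test to the group coefficient to decide whether abstinence rates in the arms are "statistically significantly different at the one-sided 0.025 level". Hypothesis 1b has its own paragraph, which gives no level. Hypothesis 2 covers two definitions: "NRT sampling will result in higher rates of quit attempts (any self-defined and any 24hr quit attempt", with neither put first. Section 4.9 mentions multiple comparisons only for differences between clinics.

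**The concern.** The Aims do not merely list things to be measured. They divide outcomes into primary and secondary, and they put quit attempts on the opposite side from 4.2. Both texts are current, and 4.9 does not settle the matter, because it names no lead hypothesis.

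What is at stake is how one plausible result would be read: abstinence not significant, quit attempts significant. Under the Aims that is success on a primary outcome. Under 4.2 it is a secondary finding in a trial whose primary outcome was null. The result is realistic on the sponsor's own evidence. The Specific Aims report that the prior sampling trial, which was powered on quit attempts, significantly increased them but showed only trends for abstinence. As the plan stands, the label could be chosen after the results are known.

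**Working it through.** **Inputs from the documents**

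- Outcomes called primary: three in the Specific Aims; one in 4.1 and 4.2.
- Test level: one-sided 0.025 (4.9). The sentence names abstinence rates. It stands in the paragraph for Hypotheses 1a, 2 and 3 and concerns the group coefficient of models fitted to each outcome, so extending it to Hypotheses 2 and 3 is a reasonable reading, though not a stated one.
- Interim look: level 0.005, with power falling from 0.80 to 0.79 (4.13 and 4.17).
- Correlation between the test statistics: not given. Values below are assumed.

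**The plan's own figure.** The plan gives no error rate across hypotheses, and the rationale for N=1300 is deferred to Section C.10 of the grant text, which is not in the documents. What can be checked is the interim statement. A two-look O'Brien-Fleming boundary at half the information has constant c = 1.977. The interim bound is 1.977 × √2 = 2.797, a two-sided level of 0.0052. With drift 1.960 + 0.842 = 2.802, power is 0.797. The stated 0.005 and 0.79 are reproduced to rounding.

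**Chance of at least one false positive if any of the three Aims primaries could carry the claim.** With independent tests:

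1 − (1 − 0.025)³ = 1 − 0.9269 = 0.0731

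The upper bound is 3 × 0.025 = 0.075. With equal correlation r between the test statistics, the chance is 1 − Φ₃(1.96, 1.96, 1.96; r), where Φ₃ is the trivariate normal distribution function:

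| Assumed r | Chance of at least one false positive | Ratio to 0.025 |
|---|---|---|
| 0 | 0.073 | 2.9 |
| 0.3 | 0.068 | 2.7 |
| 0.5 | 0.063 | 2.5 |
| 0.7 | 0.055 | 2.2 |
| 0.9 | 0.042 | 1.7 |

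**Under 4.1 and 4.2.** There is one primary test, and its error is 0.025 before any allowance for the interim look. Testing Hypotheses 2 and 3 alongside it does not change that.

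**Cost of keeping three primaries instead.** Bonferroni gives 0.025 / 3 = 0.00833 each, critical value 2.394. Power for abstinence falls from 0.80 to Φ(2.802 − 2.394) = Φ(0.408) = 0.658. Restoring 0.80 would need ((2.394 + 0.842) / 2.802)² = 1.33 times the information.

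**The case against.** The strongest reply is that the plan has one primary outcome and the Aims sentence is loose. Much supports this. The Specific Aims say that this trial is powered on abstinence; the Primary Specific Aim itself is framed around cessation outcomes; 4.1 and 4.2 are explicit; and the efficacy look in 4.13 and 4.17 is on quit rates. The Abstract speaks of aims rather than outcomes, so it is weaker evidence than the Aims sentence. Nowhere is it said that success on any one outcome makes the trial positive. All of this stands. It shows which wording to keep, and it makes the inflation conditional. It does not remove the Aims sentence, which assigns primary status to quit attempts in so many words.

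A reader might go further than the documents allow in four ways:

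- *Every hypothesis is tested at one-sided 0.025.* No level is given for Hypothesis 1b, and the sentence in 4.9 names only abstinence. A count of false positives that adds 1b and splits the two quit-attempt definitions would therefore rest on a level that the plan does not state.
- *The trial exceeds its stated error rate.* The 0.025 is a level for a test, not a promise about a family of tests.
- *The independent-tests figure is the expected one.* Someone abstinent at 6 months will normally have made a quit attempt, and 4.9 sets missing participants to neither. Positive correlation is likely, so 7.3% is near the top of the range.
- *Uptake is an easy win because the sampling arm is handed NRT.* Hypothesis 3 concerns later uptake, and the Aims speak of additional treatment. The documents do not show that the samples themselves would count.

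**Conclusion.** The contradiction over primary status is real, and section 4.9 leaves it open. Its practical effect is that a positive quit-attempt or uptake result with null abstinence can be labelled in two ways. If the Aims wording were used and any one of the three outcomes sufficed, the chance of a false primary claim would be about 4% to 7% rather than 2.5%. That range assumes that one-sided 0.025 applies to each of the three, that each test holds its level, and that correlations lie between 0 and 0.9. Under 4.1 and 4.2 the abstinence test is not inflated at all. This is a wording defect in what counts as trial success. It should be corrected before outcome data by arm are examined.

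**What to change.** 1. Reword the outcome sentence in the Specific Aims, and the primary-aims sentence in the Abstract, to match 4.1 and 4.2: Hypothesis 1a is the sole primary; Hypotheses 1b, 2 and 3 are secondary.
2. Add treatment uptake and longest abstinent period to the secondary list in 4.2. Aligning the Aims alone would leave both without a stated status there.
3. State in 4.9 that the confirmatory conclusion at one-sided 0.025 rests on Hypothesis 1a, and that the other hypotheses are reported as estimates, confidence intervals and nominal p-values. Section 4.9 already provides rates with 95% intervals for the outcomes of Hypotheses 1a, 2 and 3, so little is added.

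Naming a lead definition of quit attempt, or using Holm's method if formal secondary claims are wanted, is optional.

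The cost is text only. Sample size and power for abstinence are unchanged, unlike the Bonferroni route above. The one real loss is that a positive quit-attempt or uptake result alone could no longer be presented as a primary success.

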1.2 Sources of Materials

Research material obtained from the participants include responses to in-person and telephone-based questionnaires regarding smoking patterns, attitudes, behaviors, etc. Research data will be obtained specifically for research purposes. There will be no use of existing specimens. The consent form will include language to allow access to the participant's Electronic Medical Record (EMR) data, for up to 2 years following date of consent. Every effort will be made to maintain subject confidentiality, in accordance with HIPAA.

